11.2.4. Missing Dates in Prior and Concomitant Medication

If the start/stop dates of a medication are partially or completely missing, then the medication will be assumed to be concomitant if it cannot be shown that it was not administered during the on-treatment period. Missing dates will not be replaced.

The on-treatment period is defined as the time from the first dose to 7 days after the last dose of lonapegsomatropin/placebo or from the first dose to 1 day after last dose of daily somatropin.

11.2.5. Missing Causal Relationship to the Trial Drug for Adverse Events

If the causal relationship to the trial drug is missing for an AE that started on or after the date of the trial drug administration, a causality of “related” will be assigned. The imputed values for causal relationship to trial drug will be used for the incidence summary; the values will be shown as missing in the data listings.

11.2.6. Missing Data for Trunk Percent Fat at Week 38

If there are sufficient number ($n \geq 5$) retrieved dropouts in the lonapegsomatropin group, where retrieved dropouts are subjects who discontinued treatment prior to Week 38 but still have their measurements at Week 38, a retrieved dropout imputation method will be used to impute the missing measurement of non-retrieved dropouts based on known measurements from retrieved dropouts in the lonapegsomatropin group.

In the case where there are not sufficient numbers ($n < 5$) of retrieved dropouts, missing data in the lonapegsomatropin group will be imputed by copy reference imputation method for the subjects without final assessment at the Week 38 window (See [Table 2](#)) for the primary endpoint analysis ([Ayele 2014](#)).

Subjects with missing primary endpoint will have trunk percent fat value imputed using a multiple imputation model stratified by the treatment [[Schafer JL 1997](#), [Schafer JL 1999](#)]. Imputation of missing data will be conducted under assumption of missing not at random (MNAR). Missing not at random means that the data are missing is systematically related to the unobserved data, that is, the missingness is related to events or factors which are not measured.

In this analysis, intermittent missing values will be imputed to monotone missing pattern using the Markov Chain Monte Carlo (MCMC) methodology which assume that the joint distribution of the missing data and the model parameters are distributed multivariate normal. The variable list for imputations will include region (North America, Europe, Asia), dosing group and AGHD onset (adult vs. childhood), results from baseline and post baseline values for trunk percent fat.

Then all the monotone missing values will be multiply-imputed using the imputation model built from the placebo group, i.e., assuming the missing data in the treatment group will have a profile that equals the profile of the placebo group for all time points (i.e., a copy-reference imputation). The missing data imputation will be implemented using PROC MI in SAS 9.4 with the MNAR statement. Missing data in the daily somatropin group will be imputed following the same method as the lonapegsomatropin group. Missing data in the placebo group will be imputed using the imputation model built from the placebo group.

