8.2. PREMATURE SUBJECT WITHDRAWAL

Early withdrawal occurs when an enrolled subject ceases participation in the trial, regardless of the circumstances, prior to the expected completion of the trial (= completion of Week 38).

Additionally, the investigator may discontinue the treatment of a subject at any time if considered to be in the subject's best interest, see Section [7.3.1](#) for detailed definition.

If in any case treatment should be discontinued, all subsequent visits and assessments should continue as planned. If the only option for the subject is to drop-out of the trial, the subject may also be offered to only attend the final Visit 7.

If the subject withdraws from the trial prematurely, a Completion Visit/Early Termination Visit should be performed to collect data, particularly AE follow-up data (if applicable), and to collect blood for laboratory evaluations. This visit should contain all assessments from Visit 7 (Week 38, see Schedule of Events, Section [18.2](#)) and will be documented in the eCRF together with the reason(s) for trial withdrawal. Individual assessments may be waived if the subject refuses to participate, if they have been done recently and/or are not deemed appropriate or required. Such instances shall be discussed with the Medical Monitor. For subjects who discontinue the study drug for reasons related to safety, unblinding of the treatment assignment for the subject may occur if deemed necessary by the Sponsor to assess a potential safety signal or by the investigator to provide adequate medical care to the subject.

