4.3. TERTIARY OBJECTIVE

5. SAMPLE SIZE CONSIDERATIONS

This trial is powered for the efficacy comparison of lonapegsomatropin versus placebo. The daily somatropin product arm is included as a calibration arm and not powered for formal comparison.

Approximately 240 subjects will be randomized in a 1:1:1 ratio to once-weekly lonapegsomatropin, once-weekly placebo, or daily somatropin. However, for local regulatory requirements, recruitment may be kept open in some countries after having this number reached for the global trial.

A sample size of 80 subjects per arm in the lonapegsomatropin and placebo once-weekly treatment arms will provide 90% power to detect a treatment difference of 1.9% between once-weekly lonapegsomatropin and placebo for the primary endpoint of change from baseline in trunk percent fat at Week 38 at the 2 sided 5% significance level, with the assumption of a common SD of 3.7%.

Sample size and power calculations were performed using the software SAS v 9.4.

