11.3. VISIT TIME WINDOWS

All post-baseline visits will be mapped to the post-baseline scheduled visit with the closest target study day for each scheduled assessment with exception of DXA data, PRO, PK/PD parameters. If the unscheduled visit is in the middle of two scheduled visits, it will be mapped to the later one.

After mapping, if there is more than one visit in the same window, the visit closer to the target assessment day will be used. If more than one visit has an equal distance to the target day, then the later one will be used; if more than one visit occurs on the same day, the time or the sequence number will be used to select the later record. For listings, all data points (as observed) will be included.

Table 2: Analysis Window

Visit	Week	Target Study Day	Study Day Window
Visit 1 (Pre-dose)/Baseline	Week 1	1	<=1
Visit 2	Week 4	29	2-43
Visit 3	Week 8	57	44-71
Visit 4	Week 12	85	72-102
Visit 5	Week 17	120	103-158
Visit 6	Week 28	197	159-232
Visit 7	Week 38	267	233 - (316 or <= first dose date in the TCH-306 EXT which ever is earlier)
Safety Follow-Up ¹		Date of last dose + 28 days	Date of last dose date + 7 days - Date of last dose + 49 days

Study day is calculated with respect to the date of the first dose of trial drug (Study Day 1). Safety Follow Up visit will be included for ADA analysis collected at Safety follow up visit¹.

For the analysis of primary, secondary, tertiary endpoints and exploratory endpoints [REDACTED] assessed by DXA, following study day window will be used:

- Week 12, analysis will be performed based on the assessments performed at the scheduled visit.
- Week 38: Target Day of 267 and Study Day window from 240 - (295 or last assessment taken on or prior to the first dose date in the TCH-306 EXT, whichever is earlier)

After mapping, if there is more than one DXA assessment in the same window, the visit closer to the target assessment day will be used. If more than one DXA assessment with an equal distance to the target day, then the later one will be used in the analysis.

For the analysis of PRO [REDACTED] and PK/PD parameters including IGF-1 and IGFBP-3, analysis will be performed based on the assessments performed at the scheduled visit. For listings, all data points (as observed) will be included.

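### SAP 11.2.6 does not exclude retrieved-dropout donors scanned on drug, and gives the daily arm no clear donor rule of its own; the likely bias is small but favours the drug

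*SAP*

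**What the plan says.** SAP 11.2.6 has two branches for a missing Week 38 trunk percent fat value. With at least five retrieved dropouts in the lonapegsomatropin group, missing values there are drawn from those subjects. With fewer, copy-reference imputation from placebo is used. The definition is: "retrieved dropouts are subjects who discontinued treatment prior to Week 38 but still have their measurements at Week 38". It sets no order between stopping and scan, and no minimum time off drug.

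Four other provisions decide who can meet that definition:

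- SAP 11.3 gives the Week 38 DXA window as "Target Day of 267 and Study Day window from 240" up to 295, or up to the first extension dose if earlier.
- Protocol 8.2 says of the visit for a subject withdrawing early: "This visit should contain all assessments from Visit 7". Visit 7 includes a DXA scan (Protocol Table 5).
- Protocol 8.2 also keeps subjects who only stop treatment on their planned visits, so donors with real time off drug are expected too.
- SAP 11.2.4, written for concomitant medication, defines the on-treatment period as "the time from the first dose to 7 days after the last dose of lonapegsomatropin/placebo", or 1 day after the last daily somatropin dose.

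For the third arm, SAP 11.2.6 says only: "Missing data in the daily somatropin group will be imputed following the same method as the lonapegsomatropin group". SAP 12.10.1 sets a treatment-policy strategy for intercurrent events.

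**The concern.** Retrieved-dropout imputation is meant to show what happens to trunk fat after treatment stops. It does so only if the donors had been off drug when scanned. A subject who withdraws on, say, day 245 and is scanned at the Early Termination visit is inside the Week 38 window and may be inside the SAP's own on-treatment period. That subject meets the definition, counts toward the five and becomes a donor. The recipients have no in-window scan, so most of them left earlier. None of the listed imputation variables carries the time of discontinuation, and a subject who left before Week 12 has only a baseline scan to condition on. The error runs in one direction: early leavers are credited with more benefit than they kept.

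The daily arm raises a separate question of specification. The trigger and the donor pool are both written for the lonapegsomatropin group. Taken literally, the daily arm could be sent to the retrieved-dropout branch without adequate donors of its own, or to copy-reference although its own retrieved data exist.

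**Working it through.** **1. The plan's own figure.** SAP 5 plans 80 per arm and 90% power for a difference of 1.9 points. The other inputs are given there as: "at the 2 sided 5% significance level, with the assumption of a common SD of 3.7". SE of the difference = 3.7 × √(2/80) = 0.585. Power = Φ(1.9/0.585 − 1.96) = 90.1%. The stated 90% is reproduced, and it includes no allowance for dropout.

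**2. How much drug a late donor can have had.** The window opens 267 − 240 = 27 days before target. A subject who stops and is scanned on day 240 has had 239/266 = 90% of the treatment days and up to 35 of 38 weekly doses. A subject who misses only the last dose (37/38 = 97%) also qualifies.

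**3. Size in the lonapegsomatropin arm.** The documents give no dropout or retrieval rate, so these are assumptions:

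- stopping is uniform over 266 days;
- 90% of late stoppers are scanned in window;
- a fraction r of earlier stoppers return for the scan;
- late donors keep the full effect, earlier stoppers keep 20%;
- 8% of the arm of 80 are non-retrieved.

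Late stoppers are a share L of all stoppers: 27/266 = 0.102 counting from day 240, or 34/266 = 0.128 counting from day 233, where the general Visit 7 window in SAP Table 2 starts.

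- Late share of donors: s = 0.9L / (0.9L + (1−L)r)
- Retrieved share of stoppers: R = 0.9L + (1−L)r
- Retrieved rate in the arm: q = 0.08 × R/(1−R)
- Excess per imputed value: s × (1 − 0.2) × 1.9
- Shift in the arm mean: 0.08 × that excess

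For r = 0.5 and L = 0.102: s = 0.091/(0.091 + 0.449) = 0.17; R = 0.541; q = 0.08 × 0.541/0.459 = 0.094, or 7.5 expected donors; excess = 0.17 × 0.8 × 1.9 = 0.26; shift = 0.021.

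| r | L | late share | expected donors | P(at least 5) | excess per imputed value | shift |
|---|---|---|---|---|---|---|
| 0.1 | 0.102 | 0.50 | 1.4 | 0.01 | 0.77 | 0.061 |
| 0.1 | 0.128 | 0.57 | 1.6 | 0.02 | 0.86 | 0.069 |
| 0.2 | 0.102 | 0.34 | 2.4 | 0.09 | 0.51 | 0.041 |
| 0.2 | 0.128 | 0.40 | 2.6 | 0.12 | 0.60 | 0.048 |
| 0.5 | 0.102 | 0.17 | 7.5 | 0.88 | 0.26 | 0.021 |
| 0.5 | 0.128 | 0.21 | 7.9 | 0.90 | 0.32 | 0.025 |

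The larger shifts belong to scenarios in which five donors are seldom reached, so copy-reference would be used instead. Where the branch usually runs (r = 0.5), the shift is 0.021 to 0.025 points: 1.1% to 1.3% of 1.9, and about 4% of one SE (0.025/0.585). At r = 0.5, if earlier stoppers kept none of the effect, the shift would be s × 1.9 × 0.08 = 0.026 to 0.032; if they kept half, 0.013 to 0.016.

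**4. Ceiling.** Suppose every donor carried the full effect and the recipients truly had none. The overstatement would be 1.9 × m/80 for m missing subjects: 0.10 (m = 4), 0.19 (m = 8), 0.29 (m = 12) or 0.38 (m = 16). This requires every donor to be a late stopper.

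**5. Daily arm.** Let p be the binomial probability of at least five retrieved dropouts among 80, with the arms independent and at equal rates. The arms fall on opposite sides of the threshold with probability 2p(1−p):

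| retrieved rate | p | opposite sides |
|---|---|---|
| 2% | 0.02 | 4% |
| 3% | 0.09 | 17% |
| 5% | 0.37 | 47% |
| 6.25% | 0.57 | 49% |
| 10% | 0.91 | 16% |
| 15% | 0.995 | 1% |

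A split is not itself a bias. It shows how often the two readings of the daily-arm sentence could lead to different branches.

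**The case against.** The strongest reply has five parts.

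- **The wording describes people who have stopped.** A reader might infer that the plan deliberately takes on-drug donors and imputes early leavers with near-full drug effect. The text does not support that. It fails to exclude recent stoppers, and Protocol 8.2 should also supply donors with real time off drug. Near-full effect is the ceiling in step 4, not the expectation.
- **The route is narrow.** The scheduled scan is at Week 38 or 39. If two scans fall in the window, the one nearer day 267 is used, and assessments at early termination may be waived. Scans well before day 267 therefore come mainly from withdrawals at or after day 240. This stands, and it is a reason the late share may be lower than assumed.
- **The daily-arm sentence can mean the same procedure applied within that arm.** SAP 11.2.6 also calls the imputation model stratified by treatment. This stands. A reader might conclude that the daily arm certainly gets the wrong branch, but the documents show only that its branch is not pinned down. Protocol 14.4.1 excludes formal testing of that arm.
- **The tipping-point analysis covers it.** SAP 12.10.4 shifts imputed lonapegsomatropin values by 0 to 10 points, far more than any excess in step 3. It is a useful check on the conclusion, but it neither corrects the primary estimate nor settles the daily arm's rule.
- **The false-positive rate is not shown to suffer.** If the drug has no effect, late donors carry none either. A reader might infer type I error inflation; nothing here demonstrates it.

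**Conclusion.** Both gaps are real and the consequence is modest. The donor definition lets a few late stoppers, scanned before stopping or within the SAP's own on-treatment period, count toward the threshold and stand in for subjects who left much earlier. This can overstate the treatment-policy effect by about 0.02 to 0.03 points of 1.9 in the scenario where the branch usually runs. That figure rests on the assumed stopping pattern, retrieval rates, retained effect and 8% non-retrieved.

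For the daily arm, the rule allows two implementations. The choice mainly affects the descriptive lonapegsomatropin-versus-daily interval, not the primary test. The point is still worth settling before unblinding, because the bias favours the drug, the rule governs the primary endpoint and the repair is short.

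**What to change.** Amend SAP 11.2.6 in two places.

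1. Count and use as donors only subjects whose Week 38 DXA was taken after the end of their on-treatment period as defined in SAP 11.2.4: more than 7 days after the last weekly dose, or more than 1 day after the last daily dose. Keep other late stoppers' in-window scans in the analysis as observed values. The condition should run from last dose to scan, not from a calendar day. A rule that treatment must have ended before day 240 would reject a subject last dosed on day 234 and scanned on day 267 (33 days off), yet accept one last dosed on day 232 and scanned on day 240 (8 days off).
2. Apply the test of at least five, and the donor pool, separately within each active arm, with copy-reference as that arm's own fallback.

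The same edit could state that the placebo-based step applies only when an arm has fewer than five donors, since the paragraph describing it does not repeat that condition. It could also refer to the DXA window from day 240 instead of Table 2, where Visit 7 starts on day 233.

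The cost is a few sentences, with no change to sample size or data collection. There will be fewer donors, so copy-reference will be used more often and the estimate may be slightly less favourable. The condition also does not fully match donors to early leavers on time off drug: a donor 8 days off drug would still be accepted.

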11.3. VISIT TIME WINDOWS

All post-baseline visits will be mapped to the post-baseline scheduled visit with the closest target study day for each scheduled assessment with exception of DXA data, PRO, PK/PD parameters. If the unscheduled visit is in the middle of two scheduled visits, it will be mapped to the later one.

After mapping, if there is more than one visit in the same window, the visit closer to the target assessment day will be used. If more than one visit has an equal distance to the target day, then the later one will be used; if more than one visit occurs on the same day, the time or the sequence number will be used to select the later record. For listings, all data points (as observed) will be included.

Table 2: Analysis Window

Visit	Week	Target Study Day	Study Day Window
Visit 1 (Pre-dose)/Baseline	Week 1	1	<=1
Visit 2	Week 4	29	2-43
Visit 3	Week 8	57	44-71
Visit 4	Week 12	85	72-102
Visit 5	Week 17	120	103-158
Visit 6	Week 28	197	159-232
Visit 7	Week 38	267	233 - (316 or <= first dose date in the TCH-306 EXT which ever is earlier)
Safety Follow-Up ¹		Date of last dose + 28 days	Date of last dose date + 7 days - Date of last dose + 49 days

Study day is calculated with respect to the date of the first dose of trial drug (Study Day 1). Safety Follow Up visit will be included for ADA analysis collected at Safety follow up visit¹.

For the analysis of primary, secondary, tertiary endpoints and exploratory endpoints [REDACTED] assessed by DXA, following study day window will be used:

- Week 12, analysis will be performed based on the assessments performed at the scheduled visit.
- Week 38: Target Day of 267 and Study Day window from 240 - (295 or last assessment taken on or prior to the first dose date in the TCH-306 EXT, whichever is earlier)

After mapping, if there is more than one DXA assessment in the same window, the visit closer to the target assessment day will be used. If more than one DXA assessment with an equal distance to the target day, then the later one will be used in the analysis.

For the analysis of PRO [REDACTED] and PK/PD parameters including IGF-1 and IGFBP-3, analysis will be performed based on the assessments performed at the scheduled visit. For listings, all data points (as observed) will be included.

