34	0
35	0
36	0
37	0
38	0

For each dosing group, the dose may not exceed the dose shown for Weeks 13-38 in [Table 1](#) and [Table 2](#) at any time during the trial. In addition, during the Dose Maintenance Period, the dose may not exceed the dose assigned at V4, which may differ from dosing tables ([Table 1](#), [Table 2](#)) taking into consideration potential dose reductions during Titration Period due to tolerability or IGF-1 levels.

For all dose adjustments in all treatment arms, the site staff may inform the subject via phone or other communication methods about the new dose. The subject is not required to attend an additional in-person visit unless additional training on study drug administration is needed as determined by site staff or requested by the subject.

The trial will use dosing algorithms to ensure uniform trial design and consistent dose adjustments across ([Figure 3](#) and [Figure 4](#)).

Figure 3: Dosing Algorithm – Titration Period

(a) For subjects on the lowest dose level (█ mg hGH/week or █ mg hGH/day), instead of dose decrease, the study drug may be temporarily held or discontinued based on investigator's judgement.

[figure not shown]
(b) Considering timelines for analysis and reporting of IGF-1 levels, protocol defined up-titrations will occur at Week 5, Week 9 and Week 13 based on safety and tolerability as judged by the investigator. Once the IGF-1 result is available, it will be assessed for whether a dose decrease is warranted (ie, if average IGF-1 > 2.0 SDS) and the site will be informed accordingly. This will be done in a blinded manner as described in Section 7.1.2.1.

(c) Investigator will be informed by the unblinded team member in case of average IGF-1 SDS > 2.0, or in case of average IGF-1 SDS < 0.0 for subjects who previously had a dose decrease due to average IGF-1 SDS > 2.0. This will be done in a blinded manner as described in Section 7.1.2.1.

(d) For subjects on the lowest dose level (█ mg hGH/week or █ mg hGH/day), study drug should be discontinued.

(e) Only 1 re-challenge is allowed for subjects who previously had a dose decrease due to average IGF-1 SDS > 2.0. In case average IGF-1 SDS would rise again > 2.0 after the re-challenge, the dose will be decreased for 1 dose level (Table 3, Table 4) and will not be further increased.

Figure 4: Dosing Algorithm – Maintenance Period

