10.2.2.1. Visit Schedule of Weekly Treatment Arms (Lonapegsomatropin/Placebo)

1. Visit 1 will be performed on the day of the 1st dose (Week 1, Day 1) and all assessments will be done pre-dose, except for the injection site reaction assessment. The first dose will be given on site.
2. Visit 2 (Week 4) and Visit 3 (Week 8) will be conducted approx. 4 - 5 days post-dose (96-120 h post-dose +/- 3 hours) to be able to assess the average IGF-1 level (IGF-1 SDS) to support dose titration.
3. Visit 4 (Week 12) will be conducted approx. 4 - 5 days post-dose (96-120 h post-dose +/- 3 hours) to be able to assess the average IGF-1 level (IGF-1 SDS) to support dose titration. Subjects will be assigned their fixed dose for the next 26 weeks.
4. Visit 5 (Week 17, +/- 1 week) will be conducted on the day of the 17th dose (+/- 1 dose) to have a steady-state trough value and the upcoming dose given on site (144 – 168 h after the prior dose +/- 3 hours). All assessments (except for injection site reaction assessment) are suggested to be done pre-dose.
5. Visit 6 (Week 28, +/- 1 week) will be conducted 1-3 days post-dose (24-72 h post-dose +/- 3 hours) to have a maintenance phase sampling at approximate peak hGH and peak IGF-1 (IGF-1 SDS).
6. Visit 7 (Week 38, + 1 week, end of trial) will be conducted approx. 4 - 5 days post-dose (96-120 h post-dose +/- 3 hours) to be able to assess the average IGF-1 level (IGF-1 SDS) at the end of the trial. For subjects not participating in the extension trial: A phone call will be conducted up to 2 weeks after this visit to assess if ongoing AEs are closed. An ADA and a pregnancy test for females of childbearing potential sample will be collected approximately at least 30 days after the last study drug dose.

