10.2.3. Unscheduled Visits

Unscheduled visits are those visits that occur between regularly scheduled visits and are performed to assess a previously or currently noted AE, abnormal laboratory value(s), and/or clinical findings. In such cases, the subject will be contacted to arrange an unscheduled visit. Only focused assessments (guided by the reason for the visit) will occur at these visits. Unscheduled dose titrations may be communicated via phone and do not necessarily require an on-site visit.

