9.2. STUDY DAY

Study day will be calculated with respect to the date of the first dose of trial drug (Study Day 1). For assessments conducted on or after the date of the first dose of trial drug, study day will be calculated as:

$$(\text{Assessment date} - \text{date of first dose of trial drug}) + 1$$

For assessments conducted before the date (and time) of the first dose of trial drug, study day will be calculated as:

$$(\text{Assessment date} - \text{date of first dose of trial drug})$$

For subjects who do not receive any amount of trial drug, study day will be calculated as above with respect to the date of randomization.

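### SAP 11.3 lets an unscheduled retest soon after an on-schedule weekly-arm visit displace the scheduled safety result, and three Table 2 edges contradict the section's own midpoint rule

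*SAP*

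**What the plan says.** **SAP 11.3 and Table 2.** Post-baseline visits, including unscheduled ones, are mapped to the scheduled visit with the closest target day. DXA, PRO and PK/PD data are excepted. The targets for Visits 2 to 7 are days 29, 57, 85, 120, 197 and 267. The windows are 2-43, 44-71, 72-102, 103-158, 159-232, and 233 to day 316 or the first extension dose date if that is earlier.

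On boundaries the text says: "If the unscheduled visit is in the middle of two scheduled visits, it will be mapped to the later one". On several records in one window it says: "After mapping, if there is more than one visit in the same window, the visit closer to the target assessment day will be used". If two are equally distant, the later is used. For PRO, PK/PD and Week 12 DXA, the same section uses the assessment made at the scheduled visit.

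**Protocol 10.2.2.1 (weekly arms).** "Visit 2 (Week 4) and Visit 3 (Week 8) will be conducted approx. 4 - 5 days post-dose", and "Visit 4 (Week 12) will be conducted approx. 4 - 5 days post-dose". For the next visit: "Visit 5 (Week 17, +/- 1 week) will be conducted on the day of the 17th dose (+/- 1 dose) to have a steady-state trough value". Visit 6 is 1-3 days post-dose in Week 28, plus or minus one week. Visit 7 is 4-5 days post-dose in Week 38, with one extra week allowed.

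**Protocol 10.2.3.** Unscheduled visits are "performed to assess a previously or currently noted AE, abnormal laboratory value(s), and/or clinical findings".

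**The concern.** A closest-to-target rule is harmless when the target coincides with the planned visit day, because an on-time visit is then hard to beat. Here the targets lie after the nominal weekly-arm days, so a prompt retest tends to be closer to target than the visit that triggered it. Since unscheduled visits are made because something was abnormal, the displaced values belong mainly to subjects with abnormal results.

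At stake are the by-visit safety tables. SAP 12.12.3.1 summarises laboratory values and changes from baseline by treatment and visit. It specifies no worst-value or shift table that would bring a displaced result back, and flags out-of-range values only in listings. If the retest has normalised, the table shows less abnormality than the scheduled samples did.

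At Visits 2 to 4 there is a further wrinkle. Protocol 9.6.1 says "protocol defined up-titrations will occur at Week 5, Week 9 and Week 13", and the first doses of those weeks fall on days 29, 57 and 85, which are the SAP targets. A retest on or after the target day may therefore reflect the next dose step.

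**Working it through.** **1. Reproduce the SAP's targets and edges.** Target = 7 × week + 1. Weeks 4, 8, 12, 17, 28 and 38 give 29, 57, 85, 120, 197 and 267, all matching Table 2. Midpoints of adjacent targets are (29+57)/2 = 43, (57+85)/2 = 71, (85+120)/2 = 102.5, (120+197)/2 = 158.5 and (197+267)/2 = 232. The upper edges in Table 2 are 43, 71, 102, 158 and 232.

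**2. Nominal weekly-arm days.** SAP 9.2 makes the first dose Study Day 1, so weekly dose k falls on day 1 + 7(k-1). Doses 4, 8, 12, 17, 28 and 38 fall on days 22, 50, 78, 113, 190 and 260. The protocol ties Visit 5 to dose 17 explicitly. The Schedule of Events puts the next injection 2-3 days after Visits 2 to 4, which places those visits after doses 4, 8 and 12. For Visits 6 and 7, I take the dose of the named week. The 3-hour tolerances are ignored.

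**3. Later retests that win.** For a scheduled visit on day v and target T, with v before T, a later record on day r is chosen when |r - T| ≤ |v - T|, that is, when v < r ≤ 2T - v. For Visit 2 on day 27, 2 × 29 - 27 = 31. For Visit 5 on day 113, 2 × 120 - 113 = 127.

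| Visit | Nominal day | Target | Days before target | Scheduled day used | Displacing days |
|---|---|---|---|---|---|
| 2 | 26-27 | 29 | 2-3 | 27 | 28-31 |
| 3 | 54-55 | 57 | 2-3 | 55 | 56-59 |
| 4 | 82-83 | 85 | 2-3 | 83 | 84-87 |
| 5 | 113 | 120 | 7 | 113 | 114-127 |
| 6 | 191-193 | 197 | 4-6 | 192 | 193-202 |
| 7 | 264-265 | 267 | 2-3 | 265 | 266-269 |

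Taking the earlier nominal day widens the band (Visit 2 on day 26: days 27-32). All the bands lie inside their Table 2 windows. At Visit 7 the retest must also be no later than the first extension dose date.

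**4. Edges.** Each day from 2 to 316 was mapped by the text rule (closest target, tie to the later visit) and compared with Table 2. Exactly three days differ:

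| Day | Text rule | Table 2 |
|---|---|---|
| 43 | Visit 3 | Visit 2 |
| 71 | Visit 4 | Visit 3 |
| 232 | Visit 7 | Visit 6 |

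The other two midpoints are half-days, so no tie arises there.

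**The case against.** The strongest reply is that little is lost in practice. Displacement needs the same assessment repeated inside a narrow band, at most 6 days after a nominal Visit 2, 3, 4 or 7, and Protocol 10.2.3 limits unscheduled visits to focused assessments. All values stay in the listings. Protocol 12.3.3 requires laboratory results that are clinically significant or change treatment to be reported as adverse events. Safety reporting is descriptive. The edge conflict touches three single days, and no on-schedule visit falls near them. All of this stands and keeps the point small. It does not supply the missing rule on which record the by-visit tables should use.

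A reader might also infer more than the documents support:

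- *That every weekly-arm visit precedes its target.* Visit 1 is day 1 in both documents. Within the permitted windows, Visit 5 can fall on days 106-120, Visit 6 on 184-200 and Visit 7 on 264-272, so these can reach or, for Visits 6 and 7, pass the target.
- *That the weekly arms are affected more than the daily arm.* This is not shown. Daily-arm Visits 2 to 4 held in the named week (days 22-28, 50-56, 78-84) precede the targets by 1-7 days, against 2-3 in the weekly arms. Only at Visit 7 is the contrast clear: the day after 12 + 26 completed weeks is 7 × 38 + 1 = 267, exactly the target. Lonapegsomatropin and placebo share one schedule, so the nominal offset is the same in the main comparison.
- *That an HbA1c retest would follow an HbA1c-driven dose reduction.* Protocol 9.6.2 puts confirmation before that reduction. It sets no time for the confirmation and does not say that an unscheduled visit is needed.
- *That the targets are errors.* Day 7n + 1 means n completed weeks, which suits the daily arm's Visit 7, and Table 2 serves all three arms.

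**Conclusion.** The point holds as a minor defect in the rules for by-visit safety summaries. For on-schedule weekly-arm Visits 2 to 7, the targets lie 2-7 days late and nothing protects the scheduled record. A later repeat of the same assessment displaces it within bands of 4 days (Visit 2 on day 27) to 14 days (Visit 5 on day 113). The effect falls mainly on subjects with abnormal results. It understates a change only when the retest has normalised; a retest that confirms the abnormality does not.

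The calculation assumes visits on nominal days and an unscheduled record that contains the same assessment. The documents give no expected number of retests, so the effect on any table cannot be sized, and routine replacement of abnormal values cannot be claimed. DXA, PRO and PK/PD data, including IGF-1, are outside the Table 2 mapping, so the primary and key secondary analyses are untouched.

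The conflict on days 43, 71 and 232 is certain but editorial. Programming from the text and programming from the table would place an unscheduled record on those days in different visits.

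**What to change.** 1. In SAP 11.3, state that where a scheduled-visit record exists in the window it is used, and that an unscheduled record is used only when the scheduled one is missing. This extends to the remaining data the approach that the section already takes for PRO, PK/PD and Week 12 DXA.
2. Align the Table 2 windows with the midpoint rule: 2-42, 43-70, 71-102, 103-158, 159-231, and 232 onward with the present upper limit for Visit 7.
3. Keep the target days. Scheduled-record priority stops the displacement by itself, and moving the Visit 7 target to a weekly-arm day would take it off day 267, the daily arm's nominal day.

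The cost is SAP wording and minor reprogramming of the visit mapping. No data collection changes, and the Week 38 DXA window is not touched.
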